## **14.3 Sample Size Considerations**

The primary objective of this study is to obtain preliminary evidence of efficacy of the treatment in preventing incident moderate or greater depression defined as a QIDS-SR score greater than 11 at 12 weeks. Assuming 23 subjects per arm and a true rate of depression in the control arm of 40%, we have 80% power to detect a difference if the true rate in treatment arm is 13.8% using a one-sided alpha of 0.10. Assuming an observed rate of 40% in the control arm, the upper limit of the 80% confidence interval for the risk ratio ranges from 0.56 when the observed treatment arm rate is 10% to 1.09 when the observed treatment arm rate is 25%. Any patient who has less than 65% compliance rate after four weeks of escitalopram/placebo (as determined during bi-weekly pill diary review) will be considered not evaluable and will be replaced. Any patient who experiences a serious adverse event that requires discontinuation of study drug within the first four weeks of treatment will be considered not evaluable and will be replaced.

To achieve a final sample size of 46 (23 per arm) at 12 weeks we will randomize 55 patients allowing for up to 15% attrition.

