### **1.2 Rationale for Proposed Study**

A recent randomized study of patients with head and neck cancer offers pioneering insights into the potential benefit of this approach. Lydiatt et al. randomized 148 patients with head and neck cancer of varying stages to escitalopram (Lexapro, an SSRI, 20 mg/day, except 10 mg/day during week 1) or placebo. Patients were included in the study if they were not depressed or had mild depression at the start of treatment, as indicated by a QIDS-SR score < 11. There were minimal adverse effects in both treatment groups. Depression was more common at later time points in the placebo group compared to the treatment group (24% vs. 10%), and the benefit persisted in a multivariable analysis. Thus, the number needed to treat to prevent a single case of depression was just 7 people. Additionally, there was better quality of life noted in patients in the treatment group at every time point in the study, and as early as after 1 month of treatment. Based on this study, we will administer the same dose of study drug. We will administer escitalopram at 10 mg/day for 2 weeks, 20 mg/day for 8 weeks, and 10 mg/day for the final 2 weeks (ramp up and ramp down periods) for a total of 12 weeks.

Due to the fact that depression is more common in pancreatic cancer than any other cancer type (40% of patients), depression symptoms overlap with presenting signs and symptoms of pancreatic cancer, and depression screening is currently not standard practice for patients undergoing treatment for pancreatic cancer, the QIDS survey (nor any other tool) has been validated in the

pancreatic cancer population, we will include all patients with localized pancreatic cancer in this trial, regardless of depression score. **Importantly, patients noted to have either severe depression per the QIDS screen or suicidal ideation will be referred to a study psychiatrist for a more thorough evaluation and care plan with consideration of starting a second pharmacologic agent. However, these patients will continue on study in a blinded fashion taking placebo or escitalopram.**

We will look at QIDS scores at 12 weeks as the primary study outcome. We hypothesize that patients receiving escitalopram will have a lower rate of moderate (or worse) depression, compared to patients receiving placebo.

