#### QIDS (Quick inventory of depressive symptomatology)

QIDS is a 16-item survey that addresses each of the nine symptom domains covered in the DSM-V criteria for Major depressive disorder (depressed mood, loss of interest or pleasure, concentration/decision making, self-outlook, suicidal ideation, energy/fatigability, sleep, weight/appetite change, and psychomotor changes). The tool is used both for depression screening, and to measure depression severity, and has been heavily validated against established surveys. Its effectiveness is proven. The tool is straight forward, and is administered in either a self-reported form (SR), or a clinician-rated (CR) form, and requires minimal training. The QIDS scores range from 0-27. Scores are interpreted as follows:

0-5	No depression
6-10	Mild depression
11-15	Moderate depression
16-20	Severe depression
21-27	Very severe depression

In this study, we will be using the QIDS to measure the rate of depression at each time point, with the incidence of worsening depression at 12 weeks as a primary outcome. Patients with a QIDS score  $\geq 16$  at any time point will be referred to a psychiatrist for a more thorough evaluation and consideration for additional therapy.

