#### **Primary:**

The primary outcome measure will be depression rates, based on answers from the QIDS form. Depression is reflected by a score  $\geq 11$  (moderate depression or worse).

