### **3.1 Study Characteristics**

Patients may be non-depressed or depressed. Those who are severely depressed according to the Quick Inventory of Depression Survey (QIDS  $\geq 16$  points) will be referred to a psychiatrist for further evaluation and possibly additional therapy, based on clinical judgement. The study will be started at University Hospitals Cleveland Medical Center with the possibility that it can be opened at alternative sites if needed for patient accrual.

At the time of study enrollment, the treating physician must have the intent to treat the patient with 12 weeks of neoadjuvant chemotherapy as standard of care cancer treatment. For this study, patients will be randomized in a 1:1 ratio to receive escitalopram or placebo using a randomization table prepared by the study statistician. This randomization table will be shared by the statistician only with the Investigational Drug Services Pharmacy (IDS) personnel and will detail for all 55 patients/study IDs whether that patient is to receive escitalopram or placebo. Each patient will be

assigned a study number, in sequential order, only after all eligibility criteria have been confirmed by the study coordinator, treating physician (Investigator or Co-investigator) involved in the case, and by a member of the Clinical Trials Unit's Quality Assurance department.

It is possible that burden of disease could influence mood. Therefore, patients will also be stratified according to whether they have resectable disease or locally advanced disease (borderline resectable or unresectable) according to NCCN criteria. A pancreatic surgeon (PI or Co-Investigator) will determine this status using the Tumor Profile Assessment (see Appendix VIII). The Tumor Profile Assessment is to be filled out by the PI or by the Co-investigator prior to randomization.

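### The primary goal is worded as preventing incident or worsening depression, but the design and model estimate the 12-week depression rate in all randomized patients, including those depressed at entry

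*Combined protocol and SAP*

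**What the plan says.** The documents describe the primary target in three ways.

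- **Worsening.** Section 1.1 gives the primary goal as preventing worsening depression at 12 weeks. The QIDS part of Section 1.2 says the instrument will be used "with the incidence of worsening depression at 12 weeks as a primary outcome". No section defines worsening as a change from baseline.
- **Incident.** Section 12 defines efficacy as preventing incidents of moderate or greater depression. Section 14.1 states the hypothesis as a lower incidence at 12 weeks. Section 14.3 gives the objective as "preventing incident moderate or greater depression defined as a QIDS-SR score greater than 11 at 12 weeks".
- **Rate at 12 weeks.** The hypothesis in Section 1.2 is a lower rate of moderate or worse depression. Section 2.1 uses the rate at 12 weeks, and Section 2.4 says "The primary outcome measure will be depression rates, based on answers from the QIDS form". Section 14.2 names depression by QIDS at 12 weeks as the primary endpoint.

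On who enters: "we will include all patients with localized pancreatic cancer in this trial, regardless of depression score" (Section 1.2). Section 3.1 confirms that patients may be depressed or not. On who is analyzed: Section 14.2 analyzes all randomized patients as assigned, with baseline QIDS-SR as a continuous covariate.

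On power, for 23 per arm and a 40% control rate: "we have 80% power to detect a difference if the true rate in treatment arm is 13.8% using a one-sided alpha of 0.10" (Section 14.3).

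**The concern.** The labels would nearly coincide if depressed patients were kept out at entry. The head and neck trial described in Section 1.2 did that, with QIDS-SR below 11 required. This trial has no such limit, so the labels separate:

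| Baseline to week 12 | Event in the 14.2 model | Incident | Worse |
|---|---|---|---|
| 18 to 12 | yes | no | no |
| 3 to 9 | no | no | yes |
| 18 to 9 | no (lowers the rate) | no | no |
| 3 to 14 | yes | yes | yes |

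The first and third rows matter most. A patient who stays above the cut-off is an event without being a new case. A patient who remits lowers the arm's rate, which is treatment of existing depression and not prevention. If escitalopram only hastened remission, the primary test could succeed with no new case prevented. The trial could then claim, in the terms of Sections 12 and 14.3, a prophylactic effect that it did not estimate. Section 1.4 gives justification of prophylactic use as a benefit to the field, so the distinction bears on what a later trial would be built on.

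**Working it through.** **Step 1: does the stated power match the planned analysis?** Inputs from Section 14.3: n = 23 per arm, 40% v 13.8%, one-sided alpha 0.10 (z = 1.2816).

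- Standard error, unpooled: √[(0.40×0.60 + 0.138×0.862)/23] = 0.1249.
- Difference/SE: 0.262/0.1249 = 2.097.
- Power: Φ(2.097 − 1.2816) = Φ(0.816) = 79.3%.
- Exact binomial enumeration of the one-sided z-test: 80.1%.
- Attrition: 46/(1 − 0.15) = 54.1, rounded up to 55, as stated.

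The 80% is reproduced with all 23 patients per arm in the denominator and none removed for baseline depression. That is the comparison the Section 14.2 model makes.

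**Step 2: does any section restrict the primary analysis to patients free of depression at baseline?** No. Section 14.2 uses the baseline score as a covariate, which adjusts the comparison but removes nobody. Section 14.3 does call some patients not evaluable, but for low compliance or an early serious adverse event, not for baseline score.

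**Step 3: how many events might not be new cases?** The documents give neither the baseline share *b* above the cut-off nor the proportion *s* of those patients still above it at week 12. Assume b of 20–40% and s of 60–80%. With a 40% control rate:

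- Persistent cases as a share of control events = b×s/0.40. This runs from 0.20×0.60/0.40 = 30% to 0.40×0.80/0.40 = 80%.
- Implied rate of new cases among the rest = (0.40 − b×s)/(1 − b). This runs from (0.40 − 0.12)/0.80 = 35% to (0.40 − 0.32)/0.60 = 13.3%.

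Under these assumptions the all-patient rate and the incident rate can differ widely.

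**Step 4: power if *incident* were taken literally (illustration only).** Patients at risk per arm = 23×(1 − b). Rates are held at 40% v 13.8%.

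| b (assumed) | At risk per arm | Whole number | Exact power | Normal approximation (pooled–unpooled) |
|---|---|---|---|---|
| 20% | 18.4 | 18 | 70.1% | 70–72% |
| 30% | 16.1 | 16 | 69.3% | 66–68% |
| 40% | 13.8 | 14 | 65.1% | 61–63% |

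The normal approximation uses the fractional numbers at risk.

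**The case against.** The strongest reply is that only one event is made operational. The Section 14.3 sentence that says *incident* carries its own definition, a score threshold at 12 weeks, and Section 12 uses the same threshold. *Incidence at 12 weeks* in Section 14.1 can be read as loose usage for a rate. Sections 1.1 and 1.2 are background, and the QIDS sentence in 1.2 also says the rate will be measured at each time point. Model, population and power sentence agree with one another.

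Most of this stands, and it rules out three stronger readings.

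- *The trial is underpowered or its power figure is wrong.* The 80% reproduces for the analysis actually planned. The loss in Step 4 arises only under an incident-only analysis that no section prescribes.
- *Power would fall to about 42%.* That figure needs 14 per arm together with the head and neck trial's 24% v 10%. At those rates power is only about 50% with the full 23 per arm, so most of the drop comes from borrowing another trial's rates.
- *The 40% control rate is the background prevalence, misused as an incidence.* It equals the figure for pancreatic cancer in Section 1.2, but Section 14.3 gives no source.

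What the reply does not remove is the conflict itself. It lies in current text, in the hypothesis, the definition of efficacy and the sample size objective. *Preventing* and *worsening* are not loose words for a prevalence in a trial that enrolls depressed patients.

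**Conclusion.** The point holds as a mismatch between the stated goal and the quantity estimated. The objective, hypothesis and efficacy wording name prevention of new or worse depression; the design estimates the 12-week rate of moderate or worse depression in all randomized patients. A positive primary result would support a lower rate at 12 weeks and would not, by itself, show that new cases were prevented.

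This conclusion rests on the documents alone: open entry, all-patient analysis, and baseline as covariate only. Its numerical size does not, because the baseline share depressed is not given. The 30–80% share of persistent cases and the 65–70% incident-only power are illustrations under the assumed ranges. The stated power needs no change.

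**What to change.** In Sections 1.1, 1.2 (QIDS), 12, 14.1 and 14.3, replace *incident(s)*, *incidence of* and *worsening* with one primary event: the proportion of all randomized patients with moderate or worse depression by QIDS-SR at 12 weeks, adjusted for baseline QIDS-SR. State a single cut-off. Section 2.4 has a score of 11 or more, while Sections 12, 14.2 and 14.3 have a score above 11; these must be reconciled.

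Limit the primary conclusion to that rate. Report new cases among patients below the cut-off at baseline, by arm, as a supportive descriptive result.

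The cost is a wording amendment, made before unblinded analysis. Data collection, model and sample size are unchanged. Making prevention the primary target instead would need its own assumed rates and a new sample size. Merely to keep 23 per arm at risk after 15% attrition would take 46/(0.80×0.85), or 68 patients randomized, if 20% were depressed at baseline, and 46/(0.60×0.85), or 91, if 40% were, against the planned 55.

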### **3.2 Number of Subjects**

The clinical trial is powered for 46 patients, including 23 patients in each arm (escitalopram and placebo). However, 55 patients will be enrolled, in order to achieve the desired number due to expected attrition both before and after initiation of therapy or due to removal from study due to reasons noted in Section 6.2.

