### **3.3 Replacement of Subjects**

Patients will not be replaced.

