### **Survival**

Overall survival will be measured from the date of randomization to date of death or last follow-up, and adjusted for staging. The distribution of survival time will be estimated using the Kaplan-Meier method, and randomization groups will be compared using a stratified log-rank test.

The primary and secondary analyses will be performed on all randomized patients. Patients will be analyzed according to randomization assignment, regardless of the treatment actually received.

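### Section 14.3 replaces two groups of patients as not evaluable, while Section 3.3 and the Replacement Policy replace nobody; Section 7.0 both ends and continues follow-up after an early event

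*Combined protocol and SAP*

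**What the plan says.** **Replacement.** Section 14.3 names two groups. One is patients with "less than 65% compliance rate after four weeks of escitalopram/placebo". The other is defined by this wording: "serious adverse event that requires discontinuation of study drug within the first four weeks of treatment will be considered not evaluable and will be replaced". Section 3.3 says "Patients will not be replaced", and the Replacement Policy directly after 14.3 repeats that sentence; neither gives an exception.

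**Sample size.** Section 14.3 plans 46 patients (23 per arm) at 12 weeks and says "we will randomize 55 patients allowing for up to 15% attrition". Section 3.2 explains the surplus by attrition and "due to removal from study due to reasons noted in Section 6.2". Section 3.1 says the randomization table "will detail for all 55 patients/study IDs whether that patient is to receive escitalopram or placebo".

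**Analysis population.** At the end of the Survival part of 14.2: "The primary and secondary analyses will be performed on all randomized patients" and "Patients will be analyzed according to randomization assignment, regardless of the treatment actually received". No evaluable population is defined anywhere.

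**Follow-up.** The first paragraph of Section 7.0 removes a patient whose drug-stopping event falls in the first four weeks and says that follow-up ends. Its second paragraph keeps everyone who stops drug, whatever the reason, on all questionnaires. Section 6.1 (Unblinding Procedures) asks patients unblinded early, which includes those meeting the removal criteria of 6.2, to go on with calls and questionnaires. Section 6.2 continues surveys for those who withdraw from treatment unless they withdraw consent.

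**The concern.** Staff facing one of these patients cannot comply with every rule: they must replace the patient or not, and go on collecting questionnaires or not.

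There are two consequences for the analysis. First, if follow-up stops, the patient still belongs in the primary analysis under 14.2 but has no 12-week QIDS-SR. The result then rests on multiple imputation under missing at random, and outcomes not collected cannot be recovered later. Second, if an analyst takes *not evaluable* to mean excluded, patients leave on events that occur after randomization. Early serious events and poor compliance can depend on the assigned drug and on mood, and mood is the primary outcome. The choice between readings should not be left until the data are in.

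**Working it through.** **1. The plan's own figures.** Inputs from 14.3: 23 per arm, 40% against 13.8%, one-sided alpha 0.10. Enumerating all pairs of binomial outcomes and applying the pooled z-test gives 80.1% power, which matches the stated 80%. For attrition, 46/0.85 = 54.1, and 55 covers it. The surplus is 55 − 46 = 9, or 9/55 = 16.4%. The stated figures stand; 55 is the size of a design that absorbs losses without replacement.

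**2. How far the surplus goes.** The documents give no rate for the two 14.3 rules. If 5, 10 or 15% of the 55 met either rule (assumed), 2.75, 5.5 or 8.25 of the nine would be used, leaving 6.25, 3.5 or 0.75 for all other attrition.

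**3. What is lost if follow-up ends.** QIDS-SR is scheduled on Days 1, 8, 22, 36 and later. The Day 36 visit has a window of 7 days either way, so it opens on Day 29. A patient removed within four weeks therefore has the Day 1 baseline and at most two scheduled post-baseline scores (Days 8 and 22). This does not apply to low compliers: nothing in the protocol stops their questionnaires.

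**4. What exclusion could do.** This step applies only if *not evaluable* means excluded. All exclusion inputs are assumed: no drug effect, 40% depressed in both arms, 5% of placebo (f = 0.05) and 10, 15, 20 or 25% of escitalopram patients excluded, and a share q of the excluded depressed.

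Rate among those kept = (0.40 − f·q)/(1 − f). For example, with q = 0.60:
- placebo: (0.40 − 0.05 × 0.60)/0.95 = 38.9%
- escitalopram at f = 0.25: (0.40 − 0.25 × 0.60)/0.75 = 33.3%
- risk ratio: 33.3/38.9 = 0.86

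Type I error is the exact rejection probability of the one-sided 10% pooled z-test. Starting from 27 per arm, 24, 23, 22 or 20 escitalopram patients are compared with 26 placebo patients. Starting from 23 per arm, 21, 20, 18 or 17 are compared with 22.

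| q | Risk ratio at f = 10 / 15 / 20 / 25% | Error from 27 per arm | Error from 23 per arm |
|---|---|---|---|
| 60% | 0.97 / 0.94 / 0.90 / 0.86 | 11.9 / 13.7 / 15.5 / 18.6% | 11.5 / 13.6 / 15.0 / 19.7% |
| 40% | 1.00 throughout | 10.2 / 10.4 / 9.7 / 9.8% | 10.2 / 10.2 / 9.9 / 11.2% |
| 20% | 1.03 / 1.06 / 1.10 / 1.14 | 8.7 / 7.7 / 5.7 / 4.7% | 9.0 / 7.4 / 6.2 / 5.8% |
| No exclusion | 1.00 | 10.6% | 9.6% |

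The risk ratio is unbiased if both arms lose the same share with the same depression rate among the excluded, or if the excluded are depressed as often as the rest. The test is unadjusted; the planned adjustment for baseline QIDS-SR is not modelled.

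**The case against.** The strongest reply is that 14.2 already fixes the analysis population. *Not evaluable* appears only in a sample-size section, beside the target of 46, so it may mean no more than not counted toward 46. On that reading there is no conflict with 14.2 and no exclusion bias. This is a fair reading, and the error rates in step 4 fall away under it. They also rest wholly on assumed inputs: the largest need a 25% against 5% gap with 60% of the excluded depressed, and Section 1.2 describes few adverse effects in either arm of the earlier head and neck trial, so smaller gaps may be more likely.

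A second reply is that *replaced* could mean covered by the nine surplus patients, and *not replaced* could mean nobody added beyond 55. The text does not say so. A planned surplus is what a no-replacement design uses, and it does not make a sentence promising replacement true.

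A third is that the four-week sentence in 7.0 may be a specific exception to the general rule after it. The second paragraph allows none, since it covers every reason for stopping, and Section 6.1 asks patients unblinded on removal to continue. It is true that 6.2 speaks of withdrawal from treatment and does not clearly cover removal for an adverse event, and that the Day 1 score remains available for imputation.

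**Conclusion.** The plan is wrong as written on replacement and on follow-up, and silent on what *not evaluable* does. The two contradictions stand whatever the number of patients affected and do not depend on the error rates.

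The firmest consequence is loss of the 12-week primary outcome for patients with an early drug-stopping event, if the first paragraph of 7.0 is applied. The exclusion bias is conditional on reading the label as exclusion. Under the assumptions in step 4, one-sided type I error then ranges from 4.7 to 18.6% starting from 27 per arm, and from 5.8 to 19.7% starting from 23, around a nominal 10%. These figures show possible size, not expected size. Because the conflict decides who is analysed and whether the primary outcome is collected in a trial planned on 46 patients, it must be fixed.

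**What to change.** 1. In 14.3, delete the two sentences that make patients not evaluable and replace them. Sections 14.2, 3.3 and the Replacement Policy then govern: all randomized patients are analysed as assigned and none is replaced. An analysis restricted to at least 65% compliance may be kept as a labelled sensitivity analysis.
2. In 7.0, reconcile the sentence ending follow-up with the paragraph after it and with 6.1 and 6.2, so that stopping study drug does not by itself end collection of QIDS-SR, PHQ-9 and FACT-Hep unless consent is withdrawn.
3. The sponsor should reconcile the removal-from-study wording in 6.2, Table 7.1 and 8.2.4 with 6.1. The suicide-risk withdrawal wording in 6.2 and in the Safety Assessment part of 7.0 is also for the sponsor to reconcile; no direction is proposed. No dose or drug-stopping rule changes.

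**Cost.** Wording, plus a few questionnaires already scheduled. Keeping patients who stop drug may dilute the effect, which 14.2 already accepts. If a share s of escitalopram patients stop and get no benefit (assumed 40% rate), the arm rate is (1 − s) × 13.8% + s × 40%. For s = 5, 10 and 15% this gives 15.1, 16.4 and 17.7%. Exact power falls from 80% to 76, 72 and 68% at 23 per arm, or from 83% to 79, 75 and 71% at 27 per arm.
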